7.1 Standard definitions

An **adverse event** (AE) is any untoward medical event affecting a clinical trial participant. Each initial AE is considered for severity, causality or expectedness and may be reclassified as a serious adverse event based on prevailing circumstances.

A serious adverse event (SAE), is any AE, that:

- results in death;
- is life threatening (i.e. the subject was at risk of death at the time of the event; it does not refer to an event which hypothetically might have caused death if it were more severe);
- requires hospitalisation or prolongation of existing hospitalisation*;
- results in persistent or significant disability or incapacity;
- is otherwise considered medically significant by the investigator.

*Hospitalisation is defined as an overnight hospital admission.

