7.2 Trial specific considerations

In this trial, the following events are expected and are reported as SAEs:

- Bacteraemia/ urosepsis
- Pyelonephritis
- Allergic reactions
- Erosion (tearing) of the urethra, primarily the urinary meatus
- Creation of a false passage/ urethral fistula
- Autonomic dysreflexia
- Damage to rectum/ peritonitis
- Urethritis
- Epididymitis.

In this trial, the following events are anticipated and are captured as primary or secondary outcomes rather than being captured through adverse event or serious adverse event reporting processes.

- Catheter blockage
- S-CAUTI
- Urinary retention
- Catheter change due to other reasons such as S-CAUTI, Urinary Leakage
- Catheter twists/ kinking/ dislodgement
- Bladder pain/ spasm
- Haematuria/ pyuria
- Urethral trauma/ bleeding
- Urinary bypass/ urinary leakage/ urinary incontinence
- Bladder stones
- Urethral stricture/ narrowing
- Irritation.

Hospitalisations or prolongations of an existing hospitalisation due to any of the LTC related events listed within the primary or secondary outcomes will not be considered or recorded or reported as an SAE. They are recorded as outcomes and regularly reviewed/ monitored by the DMC.

Hospitalisations for treatment planned prior to randomisation and hospitalisation for elective treatment of a pre-existing condition will not be considered or recorded or reported as an SAE. Complications occurring during such hospitalisation will also not be considered, recorded or reported as an SAE.

In this trial, all other SAEs that are related to the catheter and associated washout procedures are recorded. In addition, all deaths (any cause) are also recorded as SAEs. Events that are serious but are not related to the catheter or associated washouts will not be recorded as SAEs.

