7.3.5 Regulatory reporting requirements

The CI or delegate reports any SAEs that are related to any of the research procedures and unexpected to the REC within 15 days of the CI becoming aware of it using the HRA SAE form. The CI or delegate is responsible for submitting annual reports to the REC on the anniversary of the approval.

All SAEs recorded within the study are summarised and reported to the Ethics Committee, the Funder, the Trial Steering Committee and the Data Monitoring Committee in their regular reports. In addition, adverse events captured as secondary outcomes (in particular S-CAUTI) will be regularly summarised and reported to the Data Monitoring Committee in their regular reports or earlier if indicated.

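### The SAE exemption for complications during planned or elective admissions has no exceptions and conflicts with section 7.2's own rules on listed events and, on its face, deaths

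*Protocol*

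**What the plan says.** Protocol section 7.2 holds several rules on what counts as an SAE in this trial.

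- **Listed events.** It opens with a list that includes bacteraemia/urosepsis, pyelonephritis, allergic reactions, false passage and peritonitis, and says that "the following events are expected and are reported as SAEs". The list is not limited by type of admission.
- **Outcome events.** A second list (blockage, S-CAUTI, urinary retention, haematuria, urethral trauma and others) is captured as primary or secondary outcomes instead. Admissions due to these are not SAEs, but are recorded as outcomes and reviewed by the DMC.
- **Planned and elective admissions.** The exemption covers "Hospitalisations for treatment planned prior to randomisation and hospitalisation for elective treatment of a pre-existing condition". It continues: "Complications occurring during such hospitalisation will also not be considered, recorded or reported as an SAE".
- **Related events.** The next paragraph says that "all other SAEs that are related to the catheter and associated washout procedures are recorded".
- **Deaths.** "In addition, all deaths (any cause) are also recorded as SAEs".
- **Unrelated events.** The last sentence excludes serious events not related to the catheter or washouts.

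Section 7.1 counts death as an SAE, and also an event that "requires hospitalisation or prolongation of existing hospitalisation", without setting planned admissions apart. Section 7.3.1 refers back to 7.2 for what is to be recorded.

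**The concern.** Not counting a pre-planned admission as an SAE is ordinary practice: the admission itself is not an untoward event. Section 7.2 goes further and exempts whatever goes wrong during the admission. It names no exception for a death, for an event on the section's own SAE list, or for an event caused by the catheter or a washout.

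The safety of washout policies is part of the research question in section 2, and section 1.1 notes concern that washouts may damage the bladder mucosa and raise the risk of infection. Serious events related to the catheter or washout are therefore the ones that the SAE process most needs to capture. Two sites could read section 7.2 in good faith and record the same event differently. The SAE summaries described in section 7.3.5 could then be incomplete in a way that no reader of those summaries could detect.

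**Working it through.** No arithmetic applies. The check sets each rule against three kinds of event arising during a planned or elective admission.

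| Event during the admission | Complications sentence | Other rule in 7.2 | Result |
|---|---|---|---|
| Event on the SAE list, e.g. urosepsis or false passage | Not an SAE | Reported as an SAE (list) | Direct conflict |
| Death as a complication | Not an SAE | Recorded as an SAE (deaths sentence) | Conflict, unless the deaths sentence overrides |
| Unlisted serious event related to catheter or washout | Not an SAE | Recorded if it is among the other related SAEs | Gap or ambiguity |

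**Does another section settle it?** No. Section 7.3.1 points back to 7.2, and section 7.1 defines an SAE without reference to planned admissions. No order of precedence is stated anywhere in section 7.

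**What does the complications sentence add?** The last sentence of 7.2 already removes serious events unrelated to the catheter or washouts. An unlisted, non-fatal surgical complication unconnected with the catheter is excluded by that rule alone. The extra effect of the complications sentence therefore falls on deaths, listed events and related events, which the rest of the section says are to be recorded.

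**Which reporting routes are affected?**

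1. Section 7.3.5 sends summaries of all recorded SAEs to the ethics committee, the funder, the TSC and the DMC. Any event left unrecorded under the exemption is missing from these.
2. Section 7.3.4 requires sponsor notification within 24 hours only for events that are serious, related and unexpected.
3. Under section 7.3.5 the chief investigator or delegate "reports any SAEs that are related to any of the research procedures and unexpected to the REC", within 15 days.
4. Section 7.3.3 judges expectedness against the events in 7.2. Events on the SAE list are therefore expected and take neither the 24-hour nor the 15-day route, whatever the type of admission.

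For listed events the possible loss is thus confined to the periodic summaries. The expedited routes are at stake only for a related and unexpected event, and for a death only if it is both.

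**What is still captured?** Blockage, S-CAUTI and the other anticipated events are recorded as outcomes. Adverse events are a secondary outcome (section 5.2), collected about monthly by diary and CRF (section 6.3). Section 7.3.5 sends adverse events captured as secondary outcomes, S-CAUTI in particular, to the DMC. The paragraph on outcome-related admissions promises capture and DMC review; the paragraph on elective admissions has no matching promise for deaths, listed SAEs or unlisted related events.

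**The case against.** The strongest reply is that site staff would read the section sensibly. The deaths sentence comes after the exemption, opens with an additive phrase and covers any cause. The same paragraph excludes unrelated serious events and yet keeps unrelated deaths, so it is natural to take it as a catch-all. That is a fair reading, and it may be the intended one. It stands as a likely resolution for deaths, but the text does not state it.

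The sentence on other related SAEs is also weak ground for a contradiction. The word other can mean what remains after the exemptions just given. That point stands: read this way, the two sentences agree. The consequence is then that a washout-related serious event during an elective admission is left out by rule, which is a safety gap even without a contradiction. The firm conflict is with the SAE list, and this objection does not touch it.

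A reader might infer more than the protocol supports:

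- *That every complication is lost.* The sentence removes SAE status only, during one class of admission, and much catheter-related morbidity is still captured as outcomes.
- *That urosepsis or peritonitis would miss expedited reporting.* Both are expected events and never enter those routes.
- *That events would follow washouts given in hospital.* The protocol does not describe inpatient washouts. The point does not need them, since harm from the catheter or from a washout before admission could appear during the stay.
- *That the missing events would be a material share of the safety signal, or would favour the washout arms.* Prophylactic washouts are the allocated policy only in arms A and B, but section 4.6 allows them later in the control arm, and catheter-related events can occur in any arm. Without admission or SAE rates, neither size nor direction can be established.

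**Conclusion.** The concern holds as a narrow defect in a stated recording rule. Section 7.2 gives opposite instructions for a listed event during a planned or elective admission. It does the same for a death, unless the deaths sentence is taken to override. For an unlisted serious event related to the catheter or washout, it leaves room for the event to go unrecorded.

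The number of events affected cannot be derived from the protocol. The practical consequence rests on the assumption that at least some sites would apply the exemption as written. The effect is on the completeness and consistency of the SAE data; the primary analysis and the sample size are not affected. The correction should be made because it concerns safety recording and costs almost nothing.

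**What to change.** Reconcile the rules in section 7.2 in one of two ways.

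1. Delete the sentence on complications and keep the exemption for the planned or elective admission itself. The section's last sentence continues to exclude unrelated serious events.
2. Keep the sentence, but state that it does not apply to deaths, to events on the section 7.2 SAE list, or to serious events related to the catheter or washout, other than those already captured as outcomes.

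The first is simpler, because a sentence narrowed as in the second would do little that the last sentence of 7.2 does not already do. Carry the same wording into the SAE guidance for sites. The cost is one sentence in the protocol and a few extra SAE forms.

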7.3 Procedures for detecting, recording, evaluating & reporting AEs, SAEs

7.3.1 Detecting AEs and SAEs

All SAEs meeting the criteria for recording within the CATHETER II study (see section 7.2) are recorded from the time a participant consents to join the CATHETER II study until their last trial follow-up. The Investigator asks about the occurrence of relevant SAEs (i.e. those that meet the criteria for recording within the CATHETER trial) at every contact with the participant or the designated person carrying out the washout.

7.3.2 Recording AEs and SAEs

When an SAE meeting the criteria for recording within the Catheter II trial occurs, it is the responsibility of the Investigator (or delegate) to review appropriate documentation (e.g. hospital notes, laboratory and diagnostic reports) related to the event. If an SAE is recorded on a participant questionnaire, the Trial office liaises with primary/secondary care to obtain further information if appropriate.

The Investigator (or delegate) will then record all relevant information about SAEs in the relevant form.

7.3.3 Evaluating AEs and SAEs

Seriousness, relatedness (causality), and expectedness is evaluated by a medically qualified individual either at the recruitment site or the Chief Investigator or delegate).

Assessment of Seriousness

The Investigator will make an assessment of seriousness as defined above.

Assessment of Relatedness (causality)

The Investigator will make an assessment of whether the SAE is likely to be related to research procedures according to the following definitions:

- **Related**: resulted from administration of a procedure required by the protocol, whether or not it is either a) the specific intervention under investigation or b) it is administered outside the study as part of normal care.
- **Unrelated**: where an event is not considered to have resulted from any of the research procedures.

Alternative causes such as natural history of the underlying disease, concomitant therapy, other risk factors and the temporal relationship of the event to the treatment are considered.

Assessment of Expectedness

When assessing expectedness refer to the expected events (Section 7.2).

7.3.4 Notification and reporting AEs and SAEs

Site staff are responsible for notifying the trial office of SAEs meeting the criteria for recording within the CATHETER II trial.

When an SAE form is uploaded onto the trial website, the Trial Manager is automatically notified. If, in the opinion of the local PI and/or the CI, the event is confirmed as being *serious* and *related* and *unexpected*, the CI or Trial Manager notifies the Sponsor within 24 hours of receiving the signed SAE notification. The Sponsor provides an assessment of the SAE. A Sponsor cannot downgrade an assessment from the PI or CI. Any disparity is resolved by further discussion between these parties.

If all the required information is not available at the time of reporting, the Investigator must ensure that any missing information is provided as soon as this becomes available. It should be indicated on the report that this information is follow-up information of a previously reported event.

7.3.5 Regulatory reporting requirements

The CI or delegate reports any SAEs that are related to any of the research procedures and unexpected to the REC within 15 days of the CI becoming aware of it using the HRA SAE form. The CI or delegate is responsible for submitting annual reports to the REC on the anniversary of the approval.

All SAEs recorded within the study are summarised and reported to the Ethics Committee, the Funder, the Trial Steering Committee and the Data Monitoring Committee in their regular reports. In addition, adverse events captured as secondary outcomes (in particular S-CAUTI) will be regularly summarised and reported to the Data Monitoring Committee in their regular reports or earlier if indicated.

8. SAMPLE SIZE AND PROPOSED RECRUITMENT RATE

8.1 Sample size

We have used information from a survey of experts and patients and also from available literature to decide that for washouts to be worthwhile there must be a reduction in LTC blockage of 25%.¹ (and personal communication). In our case this would be a reduction in the rate of blockage from 11.8 per 1000 days to 8.9 per 1000 days. Participants will be followed up for 2 years. The trial has 90% power and significance level 2.5%. The number of blockages has a negative binomial distribution with dispersion parameter 0.6. Recruiting 200 participants per arm allows for approximately 50 out of 730 loss to follow-up days. All available days of follow-up are to be used. The formula from Zhu and Lakkis[26] was used to calculate the sample size for comparing two negative binomial rates.

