The exact prevalence of LTC use is not known⁵. A study of 11 European countries showed that in the UK, 3.8% of those aged ≥65 and receiving home care routinely use a LTC⁶. Kohler-Ockmore⁷ surveyed three UK community districts and found LTC prevalence of 0.07% in adults >18 years, rising to 0.5% for those ≥75 years. 87% of the patients with a LTC had some form of chronic illness: cerebrovascular accident (26%), dementia (12%) and multiple sclerosis (11%); 26% of the patients were resident in nursing homes. The indication for catheterisation was UI in 59% and of these, 91% received a urethral catheter (UC)⁷. In 2013, the European Centre for Disease Prevention and Control conducted a point prevalence survey of healthcare-associated infections and antimicrobial use in 1181 European long-term care facilities. The mean prevalence of LTC use was 8.8%; the prevalence in England was 1.35%; Wales 5.27% and Northern Ireland 4.86%. Most recently, in May-July 2017 at the request of the trial team, colleagues in 6 English CRNs and from the Scottish Primary Care Research Network ran searches of primary care records which suggested a prevalence of 0.2-0.5% of the general population in the UK living with LTC, with approximately 20% living in care/ nursing homes. A more recent audit in Grampian showed 1045 patients with LTC on the caseload of District nurses teams i.e. prevalence of 0.26%.

LTC can be associated with several adverse events^{4, 8} which affect the daily life of patients and can consume substantial NHS resources. Wilde et al reported typical adverse events of: LTC blockage (34%), symptomatic catheter associated urinary tract infections (S-CAUTI) (57%); accidental dislodgment (28%), urinary leakage (67%), bladder spasms (59%), kinks/twists (42%), and pain 49%¹. LTC blockage and S-CAUTI in particular are physically and psychologically traumatic to patients and pose a substantial burden to NHS resources:

- LTC Blockage often occur secondary to the formation of encrustations on the luminal and outer surfaces of the catheter; with a prevalence of 40-50% in most studies^{7, 9-11}. Wilde et al in 2017¹ assessed 202 patients with LTC over 12 months and showed blockage prevalence of 34% and rate of 8.54/1000 days of catheter-use.

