4.6 Randomisation and allocation

Participants are allocated to one of the three trial arms using a centralised computerised randomisation system created by CHaRT.

Random allocation uses the minimisation covariates: Region; gender; age (< 45year, 45-64 years and \geq 65 years); residential status (care home vs community); previous blockages requiring intervention in last 6 months (0 vs \geq 1); previous S-CAUTI requiring antibiotics in last 6 months (0 vs \geq 1); Urine pH (normal vs acidic vs alkaline).

Participants will be randomised 1:1:1 to one of the following:

- Intervention arm (A): Saline washouts. A policy of weekly prophylactic normal saline (NaCl 0.9%) catheter washouts plus standard LTC care.
- Intervention arm (B): Acidic washouts. A policy of weekly prophylactic acidic (Citric acid) catheter washouts plus standard LTC care.
- Control arm (C): Standard LTC care only (i.e. no prophylactic catheter washouts)

Where deemed clinically necessary by the doctor / nurse in charge, the pragmatic design of the study permits the following changes to the washout policies:

• An increase in the frequency of the LTC washouts, at the onset of the study or following regular review during the course of the study

• A change in the type of washout, at the onset of the study or following regular review during the course of the study

• The use of prophylactic washouts in the control arm, following regular review during the course of the study (but not at the onset of the study)

These changes will be implemented and any reasons for the change recorded in the medical notes and study records. The participant will remain in the study and be followed up as per protocol.

Participants are randomised only after eligibility is confirmed and following consent.

The Principal Investigator (PI) at site, or member of the local research team (with delegated authority), accesses the web based system. Minimisation characteristics are entered into the web-based system, which returns the allocation status. Participants are informed of their allocated pathway following randomisation. If the participants are not present at the time of randomisation,

they are contacted by the research team to inform them of the allocated pathway after randomisation.

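### The planning dispersion of 0.6 has no stated source and does not fit the blockage figures the protocol cites, yet the 90% power claim rests almost wholly on it

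*Protocol*

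**What the plan says.** Section 8.1 plans for "a reduction in the rate of blockage from 11.8 per 1000 days to 8.9 per 1000 days". On error rates it says "The trial has 90% power and significance level 2.5" per cent, without saying whether the level is one-sided or two-sided. For the spread of the counts it says "The number of blockages has a negative binomial distribution with dispersion parameter 0.6". On size it says "Recruiting 200 participants per arm allows for approximately 50 out of 730 loss to follow-up days", which leaves about 680 observed days per person. A published formula "was used to calculate the sample size for comparing two negative binomial rates". The section names a survey, literature and personal communication as the basis for the 25% target, but ties no source to the 0.6.

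Section 1.1 describes a cohort study that "assessed 202 patients with LTC over 12 months and showed blockage prevalence of 34% and rate of 8.54/1000 days of catheter-use". It also describes blockage "with a prevalence of 40-50% in most studies". The cohort study is the reference that section 8.1 cites.

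Section 9 analyses the primary outcome by negative binomial regression, adjusted for the minimisation covariates. Section 4.6 lists these, and they include previous blockage in the last 6 months (0 versus 1 or more).

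**The concern.** A negative binomial model ties three quantities together: the mean count, the dispersion k (variance = mu + k·mu²) and the share of people with no event. Fixing two determines the third. The protocol cites a mean and a share affected from one cohort, and the k that these imply is far from 0.6.

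This matters because the expected counts are large. At about 8 blockages per control participant, the Poisson part of the variance is small and k dominates. If the true k is well above 0.6, the comparison is much less precise than planned. A result with no clear difference could then be presented as coming from a trial with 90% power when it says little about a 25% reduction.

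**Working it through.** **Inputs.** From section 8.1: r0 = 0.0118 and r1 = 0.0089 per day, k = 0.6, 200 per arm, t = 730 − 50 = 680 days, level 2.5%. From section 1.1: 8.54 per 1000 days and 34% over 12 months; 40-50% elsewhere.

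**Step 1: reproduce the stated power.**
- V = (1/t)(1/r0 + 1/r1) + 2k = (84.7 + 112.4)/680 + 1.2 = 0.290 + 1.2 = 1.490.
- ln(0.0089/0.0118)² = 0.0796.
- Power = Φ(√(200 × 0.0796/1.490) − z) = Φ(3.268 − z).
- One-sided 2.5% (z = 1.960): 90.5%; 197 per arm needed for 90%.
- Two-sided 2.5% (z = 2.241): 84.8%; 233 per arm needed.

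The stated 90% with 200 per arm therefore reproduces at one-sided 2.5%, with 0.6 as the multiplier of mu². The 2k term is 1.2/1.490, about 81% of V.

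**Step 2: share blocking that k = 0.6 implies.** P(at least one) = 1 − (1 + k·mu)^(−1/k).
- 8.54 per 1000 for 365 days: mu = 3.12, P = 83%.
- 11.8 per 1000 for 365 days: mu = 4.31, P = 88%.
- 11.8 per 1000 for 680 days: mu = 8.02, P = 95%.

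The cited figures are 34% and 40-50%.

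**Step 3: dispersion that the cited figures imply.** Solve (1 + 3.12k)^(−1/k) = 1 − share affected.
- 34%: k = 7.77 (share and rate from the same cohort).
- 40%: k = 5.76; 50%: k = 3.62. These are illustrative only, because the 40-50% comes from other studies with no rate or period given.

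**Step 4: unadjusted power at 200 per arm,** by the step 1 formula.

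| k | One-sided 2.5% | Two-sided 2.5% |
|---|---|---|
| 0.6 | 90% | 85% |
| 1.0 | 75% | 65% |
| 3.6 | 31% | 22% |
| 5.8 | 21% | 14% |
| 7.8 | 17% | 11% |

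For 80% power at one-sided 2.5%, k must be about 0.87 or less: V = 0.290 + 1.74 = 2.030, and √(200 × 0.0796/2.030) − 1.960 = 0.84. At 11.8 per 1000 days, k = 0.87 still means about 83% blocking within a year.

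**Step 5: optimistic allowance for covariate adjustment.** Assume that previous blockage identifies perfectly the fraction f who ever block, that the rest contribute no events, and that k = 0.6 among the blockers. The informative sample is then 200f per arm, with rates 11.8/f and 8.9/f.
- f = 0.34: V = 0.34 × 0.290 + 1.2 = 1.299; √(68 × 0.0796/1.299) = 2.04; power 53% one-sided, 42% two-sided.
- f = 0.50: power 68% one-sided, 58% two-sided.

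**The case against.** **No calculation is wrong.** This stands. A reader might infer that section 8.1 contains an arithmetic error, or that 0.6 was meant as the reciprocal of k. Step 1 rules out both, because 0.6 used as the variance multiplier returns the stated size and power.

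**Power of 11-22% is not like for like with 90%.** This also stands. A reader might set those figures against each other, but 11-22% belongs to a two-sided 2.5% level, at which the protocol's own k gives only 85%. On the reading that reproduces 90%, the range is 17-31%. The upper end of either range also borrows a 50% share from studies whose rate and period are not given.

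**A dispersion inferred from the share with no event is fragile.** In part, yes. If 34% block with k = 0.6 among them and the rest never do, the cited share and rate are matched, but the overall variance corresponds to k = (1 + 0.6)/0.34 − 1 = 3.7, not 7.8. Adjustment for previous blockage would lower the residual k further. Step 5 takes that argument to its limit and still gives only 42-68%.

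**The 34% may refer to a shorter window.** A window of about 55 days would give k = 0.6, and 60 days gives about 1.0 (power 76% one-sided, 66% two-sided). Section 1.1, however, describes the cohort as assessed over 12 months, so the annual reading is the natural one.

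**The trial population may block more often.** This is possible. Section 8.1 plans on 11.8 for this trial, and section 4.3.3 recruits some patients seen with blocked catheters. A planning rate that differs from one cohort's is not an error. But section 4.2 requires no history of blockage, and section 8.2 expects 60-70% of participants from GP practices. Even if 70% blocked within a year at 11.8 per 1000, k would be about 1.8 and power 52% one-sided or 41% two-sided.

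**The analysis estimates dispersion from the data.** True: a wrong planning k costs precision, not validity, and the confidence interval would show it.

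**Conclusion.** The point holds as an unsourced planning value that is inconsistent with the protocol's own cited data. Calling it a strict contradiction would go too far, because the trial population may differ and section 1.1 does not define prevalence. A reader might also infer that the background describes blockages as concentrated in a minority. It does not say so; it gives prevalences and a rate.

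If 34% is the share with any blockage over 12 months, k is about 7.8 and unadjusted power about 17% one-sided or 11% two-sided. An illustrative k of 3.6 gives about 31% or 22%. Optimistic assumptions about adjustment give 42-68%. Apart from a prevalence window of about 55 days, which the description of the cohort does not support, no reading tested brings power back near 90%.

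**What to change.** In section 8.1:
- give the source of 0.6 and reconcile it with the 34% and 8.54 per 1000 days in section 1.1;
- state whether the 2.5% level is one-sided or two-sided;
- replace the single 90% figure with power over a range of k, for example 0.6 to 8, and note the effect of adjusting for previous blockage.

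Also plan a pooled, arm-blind estimate of the blockage rate and dispersion from the monthly CRFs (section 6.3), and report the restated power to the TSC and DMC. The pilot check in section 8.4 covers recruitment and adherence only. At month 11, with about 100 participants and short follow-up, it may come too early to estimate dispersion well, so a later date may be needed.

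The cost is protocol wording and one blinded estimate from data already being collected. The sample size, the outcome and the analysis do not have to change. The downside is that the stated power becomes less favourable.
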